7.2.2.2 Adverse Events

Adverse events will be assessed at each visit throughout the study by open general questioning from the Investigator or study staff and entered into the CRF. The use of other medications during the study will also be noted along with the reason for use in order to capture other potential adverse effects.

8. ADVERSE EVENTS

8.1 Definitions

8.1.1 Adverse event

The term adverse event (AE) covers any sign, symptom, syndrome, or illness that appears or worsens in a subject during the period of observation in the clinical study and that may impair the well being of the subject. The term also covers laboratory findings or results of other diagnostic procedures that are considered to be clinically relevant (e.g. that require unscheduled diagnostic procedures or treatment measures, or result in withdrawal from the study). Undesirable experiences including intercurrent events (or diseases), drug reactions and clinical abnormalities or clinically significant laboratory test abnormalities, which occur during the course of a trial, are also included.

The AE may be:

- A new illness
- Worsening of a sign or symptom of the condition under treatment or of a concomitant illness
- An effect of a comparator drug
- Unrelated to participation in the clinical study
- A combination of one or more of these factors

Thus, no causal relationship with the study medication is implied by the use of the term “adverse event”. Surgical procedures themselves are not adverse events; they are therapeutic measures for conditions that require surgery. The condition for which the surgery is required may be an adverse event. Planned surgical measures permitted by the study protocol and the conditions leading to these measures are not adverse events. (See Appendix 4 - Definitions of causality and severity of adverse events).

Interviews concerning AEs must be conducted with regard to objectivity. Questions must be phrased so that they do not, by suggestion, lead the subject into giving information, which is not valid. The investigator must carefully evaluate the response and comments of the subject in order that he or she may judge the true nature and severity of the adverse event.

8.2.2 Serious adverse event

A serious adverse event (SAE) is any AE that occurs at any dose of the study medication or at any time during the period of observation that:

- Results in death
- Is immediately life threatening
- Requires or prolongs hospitalisation
- Results in persistent or significant disability or incapacity
- Occurs with overdose
- Involves cancer
- Involves congenital anomaly/birth defects
- Is medically important
- Requires medical intervention to prevent permanent impairment or damage

“Medically important” events are events that may not be immediately life threatening or result in death or hospitalisation, but may jeopardise the subject or require intervention to prevent one of the other outcomes listed in the definition above. Examples of such events are intensive treatment in an emergency room for allergic bronchospasm, blood dyscrasias or convulsions that do not result in hospitalisation, or development of drug dependency or drug abuse. Such events should be documented and reported as SAEs.

Events “requiring medical intervention to prevent permanent impairment or damage” are events where the investigator believes that medical or surgical intervention is necessary to preclude permanent impairment of a body function or to prevent damage to a body structure.

As there is an overlap between the terms “medically important event” and events requiring medical intervention to prevent permanent impairment or damage, it is left to the discretion of the investigator to select the more applicable of the two criteria when completing the “Serious adverse event form”.

All AEs observed by the investigator or reported by the subject whether or not considered related to the test medication will be followed up by the investigator until resolution, stabilisation or lost to follow up.

All AEs will be reported in the adverse event forms of the CRF and assessed by the investigator in terms of severity and relationship to the test medication. The outcome of the adverse event as well as the measures taken as a result of this event will be described in the adverse event form of the case record form.

8.2 Period of observation

AEs fall into the categories non-serious and serious (see section 8.1.2 serious adverse event). The period of observation for adverse events extends from the time the subject gives his informed consent, until he/she undergoes the final clinical examination scheduled in the study. All AEs unresolved at the final clinical examination will be monitored until they resolve or are clearly determined to be due to a subject's stable or chronic condition, or intercurrent illness(es).

Adverse events occurring after this period of observation are to be reported if the investigator feels that there is a causal relationship to the test medication.

8.3 Documentation and Reporting of Adverse Events by the Investigator

All AEs that occur after the subject has signed the informed consent document must be documented on the pages provided in the CRF. The adverse events must also be recorded in the subject's medical records.

The following approach will be taken to documentation:

- All SAEs must be documented on "Serious Adverse Event" forms.
- Non-serious AEs must be documented in the adverse event forms supplied in the CRF.
- Subjects should be encouraged to note adverse events and discuss them at their next visit or to report any event of concern to the investigator immediately.
- Every attempt should be made to describe the AE in terms of a diagnosis. If appropriate, component symptoms should also be listed below the diagnosis. If only non-specific signs or symptoms are present, these should be recorded as a diagnosis.
- For each event occurring after the first dose of study medication/randomisation, the investigator will classify whether the event is to be considered treatment emergent and whether there is a reasonable possibility that the event was associated with the use of the study medication.

An AE that occurs during the study after the first dose of study medication/randomisation will be considered as treatment emergent if (1) it was not present at the time of the first dose of study medication/randomisation and is not a chronic condition that is part of the subject's history, or (2) it was present at the time of the first dose of the study medication/randomisation or as part of the subject's medical history, but its intensity (severity or frequency) has worsened after the first dose of study medication/randomisation.

AEs that fulfil the criteria for seriousness (section 8.1.2 serious adverse event) have to be reported to the sponsor immediately (for procedure see Section 8.4 Immediate reporting by investigator to sponsor).

AEs that do not fulfil the criteria for immediate reporting will be supplied to the sponsor in the same way as all other CRF pages.

All subjects who have AEs -whether considered associated with the use of the study medication or not-must be monitored to determine the outcome. The clinical course of the adverse event will be followed up according to accepted standards of medical practice- even after the end of the period of observation-until a satisfactory explanation is found or the investigator considers it medically justifiable to terminate follow-up. Should the adverse event result in death, a full pathologist's report should be supplied, if possible.

All questions on the completion and supply of adverse event forms and any further forms issued to the investigator at a later date to clarify unresolved issues should be addressed to the sponsor.

8.4 Immediate Reporting by Investigator to Sponsor

Serious adverse events must be documented on "Serious adverse event" forms and supplied to the sponsor within 24 hours or at the latest on the following working day. The investigator must also inform the site monitor in all cases. The sponsor will ensure all legal reporting requirements are met.

Serious Adverse Events should be reported to:
[name]
CDD
[name] or [name]

The initial report must be as complete as possible, including details of current illnesses and (serious) adverse events and assessment of the causal relationship between the event and the study medication. Copies of the case report form pages containing the following information (if not already supplied to the sponsor) must be sent with the "Serious adverse event" form:

- Demography
- Medical and surgical history
- Previous and concomitant medication
- Study medication administration record

The forms documenting all non-serious adverse events that have occurred up to the time of occurrence of a serious adverse event, even if still incomplete, must also be sent with the "Serious adverse event" form.

Information not available at the time of the initial report (e.g. an end date for the adverse event or laboratory values received after the report) must be documented on a follow-up "Serious adverse event" form that carries the number(s) of the initial report(s).

The principal investigator at each site will be responsible for reporting SAE's at their site. The principal investigator at Liverpool Hospital (lead site) will be responsible for reporting all SAE's to the Human Research Ethics Committee.

8.5 Data and Safety Monitoring Board

The Data and Safety Monitoring Board (DSMB) will monitor participant safety, data quality and evaluate progress of the study. The DSMB will be composed of 3 members including a biostatistician. They monitor the safety of the study and will advise on the conduct and the ongoing validity of the trial.

[name] will be the nominated DSMB contact and will be responsible for communication between the DSMB and the Sponsor, Study Sites (and relevant personnel), Ethics committee and Investigators.

9. WITHDRAWALS AND DEFAULTERS

Subjects may be withdrawn from study medication for the following reasons:

- Determined to be necessary as per investigator, including:
 - Due to AE or SAE
 - Development of any exclusion criteria may be cause for discontinuation
 - Treatment with prohibited medications
 - Female participants fall pregnant or female partners of male participants fall pregnant
 - Subject lost to follow up (does not complete all Study visits and Study staff have failed to make contact with the subject nor arrange a successful visit for a period of 1 month past a scheduled Study visit).
 - If, in the investigators opinion continuation in the study would be detrimental to the subjects well-being

- Subjects are free to withdraw consent at any time.

In all cases the reason for withdrawal, if given, must be recorded in the Case Report Form and in the subject's medical records. The subject must be followed up to establish whether the reason was an adverse event, and if so, this must be reported in accordance with the procedures in section 8 Adverse Events.

Every effort will be made to follow up subjects who withdraw or are withdrawn from the study. All subjects withdrawn or who choose to withdraw consent will be asked to return to the study site to undergo final EOT study procedures, or as far as possible, all safety examinations scheduled for the final EOT visit for all subjects who taken at least one dose of the study drug/s. This is especially important for those subjects who withdraw due to AEs or SAEs, in order to allow for collection of detailed safety data in accordance with the procedures in section 8 Adverse Events. These subjects should be given appropriate care under medical supervision until the symptoms of any AE resolve, or the subject's condition becomes stable. Subjects may then be contacted at the end of the study for final safety monitoring procedures.

While primary analysis will be of all consenting subjects, a secondary 'on-treatment' analysis will be performed on subjects who remain compliant at the end of the 90-day endpoint.

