In subjects with stable coronary heart disease (CHD) and inducible ischemia, percutaneous coronary interventions (PCI) can improve symptoms. As coronary angiography is often inexact in accurately determining the functional significance of non-critical coronary stenoses, fractional flow reserve (FFR) can assess their physiological significance¹². For subjects with acute coronary syndromes and multivessel disease undergoing an early invasive strategy, performing PCI in the culprit vessel and 'staging' possible treatment allows measurement of non culprit FFR at initial angiography. While non-culprit FFR in Acute Coronary Syndrome (ACS) subjects may worsen acutely due to endothelial dysfunction, randomisation should minimise confounding. Return for planned staged PCI as guided by angiography has been standard practice in such subjects, and increasingly, revascularisation is FFR guided. We plan to perform another FFR study to evaluate flow changes over a three month period.

The coronary circulation is comprised of two major components: the major epicardial coronary arteries which have a capacitance function; and the microvascular circulation comprised of pre-arterioles and arterioles which provide a metabolic interface with cardiac myocytes.¹³ Both components of the circulation have been implicated in coronary ischaemia. By measuring pressure and flow in the epicardial coronary artery, indices to assess the microcirculation can be calculated such as CFR, IMR, HSR, HMR at the same time as calculating the FFR value. This provides a comprehensive physiological assessment of the entire coronary circulation¹⁴. We plan to record pressure and flow indices at the time of measurement of FFR in the culprit and non-culprit arteries.

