3. STUDY DESIGN

This is a Phase II a, prospective study comprising of 60 subjects referred to Liverpool Hospital and Sydney Southwest Private Hospital who have paired FFR assessments. To achieve this number, assuming a dropout rate of 25%, approximately 80 subjects will be approached. These subjects will be undergoing investigation for **symptomatic CHD**. Once consent has been obtained and the subject has met all the inclusion criteria without exclusions, they will be included in the study. The study is a randomised, placebo controlled trial at a randomisation rate of 1:1.

The primary endpoint will be a 20% reduction in the rate of FFR <0.80 in subjects planned to undergo staged PCI at 3 months among those randomly assigned to ACAC therapy. That is a difference of 6 or more in the ACAC group who had an FFR <0.80 at onset will have a FFR ≥0.80 at 3 months than in control group.

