5. STUDY PRODUCT

5.1 Dosage Schedule

The treatment will be administered as 50mg capsules of doxycycline, 250mg capsules of azithromycin and 150mg of rifabutin twice daily (morning and evening). The total number of capsules taken is 3 capsules a day in the first week then 6 capsules a day to be taken after food, with plenty of fluids, until the end of dosing period.

The treatment is to be on a dose escalation schedule, taken as per the following schedule:

Week 1 (Day 1 to Day 7)

Time	Doxycycline	Azithromycin	Rifabutin
Breakfast	50mg	250mg	150mg
Dinner			

Week 2 until EOT (Day 8 to Day 90)

Time	Doxycycline	Azithromycin	Rifabutin
Breakfast	50mg	250mg	150mg
Dinner	50mg	250mg	150mg

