7.1.3 Visit 3 – End of Treatment (Day 90 ± 21)

At this visit the Subject will be asked to report on current symptoms, changes to concomitant medications, and adverse events. A blood sample will be collected for laboratory tests. Subject will undergo a physical examination. The following assessments will also be performed:

- FBC, ESR and EUC
- LFT and Lipid Studies
- CK-MB, high sensitivity Troponin T
- High sensitivity CRP
- *Chlamydophila pneumoniae* macrophage cultures
- *C. pneumoniae* titer measurement
- *C. pneumoniae* DNA detection using LAMP
- Symptomatology record
- Physical examination
- Vital Signs
- ECG
- Angiogram
- Fractional Flow Reserve Study and pressure/flow measurements
- IVUS and OCT of culprit and non-culprit arteries (sub-study)
- Functional status – New York Heart Association Class

The Subject will be required to return all unused medication, and all used empty packaging for assessment of compliance. Subjects will also be required to return diaries for review and collection.

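### Section 9 does not secure a 3-month FFR for subjects who stop study drug early, and it is undefined whether an off-window FFR counts in the primary analysis

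*Combined protocol and SAP*

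**What the plan says.** - **Who is covered.** Section 9 opens with "Subjects may be withdrawn from study medication for the following reasons", but the later text speaks of leaving the study and applies one procedure to all withdrawn subjects.
- **What happens to them.** They "will be asked to return to the study site to undergo final EOT study procedures". The same sentence then gives a lesser alternative, limited to safety: "or as far as possible, all safety examinations scheduled for the final EOT visit". No day or window is given for this return. Afterwards, "Subjects may then be contacted at the end of the study for final safety monitoring procedures".
- **What EOT means.** The abbreviation list says End of Trial. Section 5.1 heads its dosing table "Week 2 until EOT (Day 8 to Day 90", which puts EOT at the end of dosing. The heading "7.1.3 Visit 3 – End of Treatment (Day 90 ± 21" ties the same phase to Visit 3, where angiogram and FFR are done. Visit 4 (Section 7.1.4, Day 180) ends participation and has no FFR.
- **The endpoint.** Section 3 sets the primary endpoint on FFR "in subjects planned to undergo staged PCI at 3 months".
- **The analysis set.** Section 11.1 admits only subjects with paired FFR to the primary analysis. Section 9 says the primary analysis covers everyone who consented.
- **Enrolment.** Section 4.3 enrols until 60 subjects have paired FFR per protocol. Section 4.4 lets withdrawn subjects be replaced.

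**The concern.** Stopping a drug is not the same as leaving a trial. In an intention-to-treat comparison, a subject who stops drug but still consents should be measured at the same time as everyone else. Nothing in the protocol says so here. The second FFR of an early stopper depends on how a site reads an undated instruction with a safety-only alternative.

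Two things are at stake. If the FFR is taken early and counted, the interval between readings may differ by arm. Section 1.1 says that non-culprit FFR in acute coronary syndrome "may worsen acutely due to endothelial dysfunction" and relies on randomisation against confounding. Randomisation balances the baseline; it does not balance a reading time that drug stopping determines. If the FFR is not taken, the subject leaves the primary analysis for a reason that may be related to treatment. Unequal stopping is plausible on the protocol's own terms: the dose escalation is there to limit adverse effects, and adverse events are the first withdrawal reason listed in Section 9.

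**Working it through.** **1. The plan's own figures.** Section 3 gives 60 subjects with paired FFR, 25% dropout and 80 approached. 60 / (1 − 0.25) = 80, which reproduces. The allowance is 80 − 60 = 20 subjects. The target difference of 6 also reproduces: 0.20 × 30 per arm = 6.

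**2. What a site could do with a subject who stops drug early.**
- *Early FFR.* EOT is read as the Visit 3 procedures and the return takes place soon after stopping. The value falls outside Day 90 ± 21. No rule says whether it is paired.
- *FFR on time.* The return is booked at Day 90. Section 9 does not exclude this, but does not require it.
- *No FFR.* Only the safety examinations are done. Section 9 permits this whichever meaning EOT has.

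The text decides between none of these.

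**3. If the FFR is missing.** If all 20 were early stoppers without a second FFR, 20 / 80 = 25% would leave the primary analysis (40 to 30 per arm if evenly split). This is an upper bound under the plan's dropout, and it takes the 80 as randomised. The documents do not split the 25% by cause.

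**4. If the FFR is early and counted.** With no drug effect:

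bias = (difference between arms in share read early) × (recovery lost by reading early).

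Neither factor is in the documents. Assumed values of 0.10 × 0.10 and 0.30 × 0.20 give 1 and 6 percentage points, or 0.3 and 1.8 subjects of 30. These show the mechanism only.

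**5. Dilution.** Let a share w of active subjects show no effect in their counted FFR. The expected difference is 20 × (1 − w) points: 6 of 30 at w = 0, 5.4 at w = 0.10, 4.5 at w = 0.25. Exact power of the two-sided Fisher test at 0.05 follows. The control rate of FFR ≥0.80 at 3 months and w are assumptions.

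| Control rate | 30/arm, w = 0 | 30/arm, w = 0.10 | 30/arm, w = 0.25 | 40/arm, w = 0.25 |
|---|---|---|---|---|
| 5% | 43.6% | 35.5% | 24.1% | 41.1% |
| 10% | 37.2% | 30.5% | 21.3% | 33.4% |
| 20% | 29.8% | 24.5% | 17.6% | 24.5% |
| 30% | 25.9% | 21.1% | 15.0% | 21.2% |

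The w = 0 column also describes losing all 20 stoppers with no selection effect. The last column describes keeping all 20 with no effect in a quarter of the active arm. Power is slightly lower there, so the reason to retain stoppers is validity, not power. If enrolment still closed at 60 pairs that included them, the 30/arm, w = 0.25 column would apply.

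**The case against.** The strongest reply is that this is a gap in wording and not a demonstrated bias. Most of its parts are fair.

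- A reader might infer that the FFR is taken on the withdrawal date. Section 9 gives no day. The later contact at study end suggests an early return, but that sentence directly follows care until adverse events settle, so it does not fix the timing.
- A reader might infer that EOT means End of Trial, so that no FFR is done. Only the abbreviation list supports this; Sections 5.1 and 7.1.3 point to Day 90. The FFR can be missed for another reason, the safety-only alternative.
- A reader might infer that early readings count toward the 60. Section 4.3 says per protocol, Visit 3 has a window, and the dropout arithmetic treats dropouts as unpaired. Yet an FFR done under Section 9 is arguably per protocol too, and no rule settles it.
- The secondary analysis of subjects compliant at the 90-day endpoint suggests that non-compliant subjects can reach Visit 3. That shows the two groups are blurred; it does not guarantee the FFR.
- If early readings are worse and more frequent on active drug, the bias runs against the antibiotics and would not create a false positive. That is right for the early branch. For the missing branch the direction is unknown.

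The study is described as feasibility work, but Section 11.2 also declares efficacy at p < 0.05, so the integrity of the comparison still matters.

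**Conclusion.** The point holds as an undefined procedure that reaches the primary analysis. For a subject who stops drug early, the second FFR may be early, on time or missing, and its status as a paired 3-month value is not stated. The conflict between Section 9 and Section 11.1 on the primary set matters most for exactly these subjects.

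The only size the documents support is a ceiling: 20 of 80 subjects, if the whole 25% dropout were early stoppers. The stronger claim of a known timing bias of some percentage points is not supported, because both of its factors are assumed. In equal arms with 25% early stopping overall, a 30-point difference would need 40% against 10%, with every stopper accepting early repeat catheterisation. The recovery argument also concerns acute coronary syndrome, while the inclusion criteria admit ischaemia without it.

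The change should be made: it is cheap and protects the randomised comparison.

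**What to change.** 1. In Section 9, separate stopping study drug from withdrawing consent. Keep every subject who stops drug but still consents in follow-up, with the study FFR and angiogram at the scheduled Visit 3, at the staged procedure already planned, and include them in the primary analysis as randomised.
2. Limit the return visit at drug stop to the safety examinations that Section 9 already allows.
3. Record the date of every second FFR. Where a procedure was clinically needed before the Visit 3 window, do not silently drop the subject: exclusion would select on an outcome-related event after randomisation. Prespecify how the value is handled, and report a sensitivity analysis with and without off-window values. State whether such pairs count toward the 60 in Section 4.3.
4. Use EOT in one sense throughout, and reconcile the primary analysis set in Section 9 with that in Section 11.1.

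The timing of clinical procedures stays with the treating team.

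**Cost.** Protocol wording and one sensitivity analysis. Some drug stoppers attend one more visit. The scheduled FFR uses a procedure already planned at 3 months. Off-drug readings may dilute the effect, as the power table shows.
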